An Observational Study of Beta-Blocker Use in Patients with Chronic Obstructive Pulmonary Disease (COPD) and Acute Myocardial Infarction

Version 4.0

May 20, 2020

1. Introduction

Chronic obstructive pulmonary disease (COPD) is the third leading cause of death worldwide and a major contributor to morbidity and mortality is comorbid cardiovascular disease. COPD is an independent risk factor for coronary artery disease and myocardial infarction (MI) is a common cause of death in those with the disease. Beta-blockers have been demonstrated to reduce the risk of death and reinfarction after MI and though observational studies suggest that this benefit extends to patients with COPD, this has not been definitively proven in randomized controlled trials. Results of the recently published randomized, placebo-controlled trial, Metoprolol for the Prevention of Acute Exacerbations of COPD (BLOCK COPD), demonstrate that beta-blockers do not reduce the risk of COPD exacerbations and increase the risk of exacerbations requiring hospitalization raising questions about the overall risk-benefit of the drugs in COPD patients, including those with class I indications such as MI. We propose a multicenter, observational study to examine the association between beta-blocker use and all-cause mortality and hospitalization following MI in patients with COPD.

2. Background

Results and Clinical Implications of the BLOCK COPD Trial

Chronic obstructive pulmonary disease (COPD) is the third leading cause of death worldwide and the majority of COPD-related morbidity, mortality and healthcare costs are driven by exacerbations, particularly those requiring hospitalization (1, 2). Possible explanations for the failure of existing treatments to control exacerbations adequately include the fact that events may be triggered or made more severe by underlying cardiovascular disease(3). Compared to age-matched controls, COPD is associated with up to a 5-fold risk of cardiovascular disease(4) which is a risk factor for exacerbation (5), hospitalization for exacerbation (6), in-hospital mortality (7, 8), and reduced survival (9, 10).

It is well established that beta-blockers reduce mortality in patients after myocardial infarction(11) and in the presence of heart failure.(12) Patients with COPD are often denied this class of medications, even in the presence of evidence based indications for their use, because of concerns about possible adverse effects on lung function.(13, 14) This practice pattern persists despite multiple observational studies suggesting beta-blockers benefit patients with COPD and comorbid cardiovascular disease with outcomes comparable to those observed in patients without COPD (13, 15, 16). Recent non-randomized studies also suggest that beta-blockers reduce the risk of exacerbations and mortality in patients with COPD, with or without known cardiac disease.(17-20) However, these observational data are subject to biases, precluding conclusions about cause and effect (21).

To address these issues, we investigated the effect of metoprolol on the risk of exacerbations in COPD patients at high risk for those events (ClinicalTrials.gov number: NCT02587351) (22, 23). We hypothesized that metoprolol would reduce the risk of exacerbations compared with placebo and would not adversely impact lung function, six-minute walk distance, dyspnea, or quality of life.

We randomized 532 participants with a mean (\pm SD) age of 65.0 ± 7.8 years and FEV₁ of 41.1 ± 16.3 % predicted. The study was stopped early due to futility for the primary endpoint and safety concerns. There was no difference in time to first exacerbation between groups and the hazard ratio (HR) for assignment to metoprolol was 1.05 (95%CI: 0.84-1.32; p=0.66). Metoprolol was associated with a higher risk of exacerbation requiring hospitalization (HR 1.91, 95%CI: 1.29-2.83). Patient reported possible beta-blocker side effects were similar between groups as was

the overall rate of non-respiratory serious adverse events. During the treatment period, we observed 11 deaths in the metoprolol group and 5 in the placebo group.

The results of the study strongly indicate that patients with COPD and at risk for exacerbation should not be prescribed beta-blockers in the absence of an established indication for the drugs such as recent myocardial infarction or heart failure.

Unanswered Questions and the Rationale for the Proposed Study

As noted above, retrospective observational studies have suggested that the benefits of beta-blockers in patients with recent myocardial infarction and heart failure extend to those with COPD (13, 15, 19, 24), however, this has not been prospectively confirmed and randomized trials in those settings may be needed to assess overall risk-benefit. Though such trials are beyond the scope of the current award, we do have the opportunity to conduct a prospective, observational cohort study to examine cardiac and pulmonary outcomes in COPD patients hospitalized for acute myocardial infarction who are and are not treated with beta-blockers.

Several large randomized trials published in the 1980s demonstrated the clinical efficacy of beta-blockers following MI but COPD patients were largely excluded from these trials because of concerns about adverse respiratory effects. For example, the Metoprolol in Acute Myocardial Infarction (MIAMI) trial excluded patients with COPD who required steroids or beta-agonists (25). The Beta-Blocker Heart Attack Trial (BHAT) excluded patients with both asthma and COPD if they required therapy (24) and the Norwegian Timolol Study excluded all patients with COPD(11). As such, these data do not provide confidence that the benefits observed in patients without COPD extend to those with the disease, particularly those with more symptoms and requiring respiratory treatments.

A number of observational studies examining this issue have been conducted in an effort to provide evidence that can guide clinician decision making but these have been limited by their retrospective design, poor characterization of the COPD patients enrolled, and a lack of adequate follow-up data about pulmonary outcomes including COPD exacerbations.

Gottlieb et al. examined the medical records of more than 200,000 patients with MI as part of the Cooperative Cardiovascular Project (CCP) and found that though beta-blocker use was less common in those with underlying COPD (22% vs. 34%), the overall benefit of beta-blockers on mortality was comparable to that observed in those without COPD (Relative Risk (RR) 0.60; 95%CI, 0.57-0.63).(15) However, no information about the severity of the underlying lung disease was available and the possibility that healthier patients received beta-blockers cannot be excluded. A second study examining data from the CCP did stratify patients with COPD based on whether they were receiving beta-agonists or had been treated with oral steroids or admitted for COPD in the year prior to their MI.(24) In that analysis, COPD patients without these characteristics derived the same mortality benefit from beta-blockers as did patients without COPD (RR 0.85; 95%CI, 0.73-1.00) but no benefit was observed in those treated with beta-agonists or treated for acute symptoms in the year prior. A more recent population-based cohort study from the UK of 1063 patients with COPD and MI occurring between 2003 and 2008 found that treatment with beta-blockers in the hospital, or at the time of discharge, was associated with improved survival compared to no beta-blocker treatment(13). Though this analysis adjusted for COPD severity as assessed by treatment, symptoms and exacerbation history, a large number of patients were excluded as beta-blocker treatment was viewed as contraindicated by the treating physician, in some cases due to COPD. This precludes examination of outcomes in this likely more severely affected group.

The results of our proposed observational study would provide more robust and contemporary data regarding the overall risk-benefit of beta-blockers in COPD patients with acute MI and provide preliminary data about the feasibility of recruitment for a subsequent randomized trial.

3. Specific Aims

Specific Aim 1. To determine the prevalence of COPD in patients admitted to the hospital with an acute myocardial infarction (AMI) and to characterize the phenotypic expression and severity of their underlying lung disease.

Patients admitted to the hospital and who undergo cardiac catheterization for an AMI will be identified through the electronic medical record (EMR). Those with a diagnosis of COPD in the EMR will be offered participation in the study. Baseline characterization will include demographics, smoking history, prior history of exacerbations in the year before admission, supplemental oxygen use, respiratory and cardiac medication use, comorbidities including history of coronary artery disease, heart failure and ejection fraction, and pulmonary function data as available in the EMR. Results of this Aim will provide data about the prevalence and clinical characteristics of COPD in the hospitalized population with AMI in our network. The Aim will also provide an estimate of the number of annual admissions for patients with COPD and AMI.

Specific Aim 2. To determine the association between beta-blocker use at discharge and cardiopulmonary outcomes in patients with COPD and AMI.

Patients with AMI and EMR-documented COPD will be followed, prospectively from the time of discharge using review of the electronic medical record and as local guidance permits, phone calls at 3 and 6 months. We will determine the associations between beta-blocker use at discharge and the risk for all-cause mortality, recurrent ischemic events, and hospitalization for COPD exacerbation adjusting for baseline characteristics and COPD severity.

4. Study Design and Methods

- a) **Overview.** The study is a prospective, observational study of patients admitted to the BLOCK COPD network hospitals with acute AMI and COPD. Patients with will be identified via the EMR. Because of the current COVID-19 pandemic and the possibility of limited access to hospitalized patients, the study consists of three options for enrollment. Option 1 or 2 is preferable if local guidance permits.

Option 1: A total of 3 visits including 1 in person visit in the hospital and 2 follow up phone calls with EMR review at 3 and 6 months after discharge. Sites may consider alternatives to in person consent and data collection including by telephone or video conference.

Option 2: EMR review at the time of hospital admission followed by post-discharge telephone consent and 2 follow up phone calls with EMR review at 3 and 6 months.

Option 3: EMR review at the time of hospital admission and follow-up review of the EMR at 3 and 6 months after discharge.

b) **Participant selection and eligibility.** Subjects hospitalized and who undergo cardiac catheterization with AMI and have EMR-documented COPD will be eligible for participation. The age, race, gender, smoking status and comorbidities of patients with who undergo cardiac catheterization for AMI but have no EMR-documented diagnosis of COPD will be recorded but no other information will be collected on this population.

c) **Inclusion Criteria**

- a. Willing and able to provide informed consent (applicable for Option 1 and 2 only)
- b. Men and women age 35 or older
- c. Admitted to hospital from the Emergency Department or by hospital to hospital transfer with a primary diagnosis of AMI
- d. Undergo cardiac catheterization for AMI
- e. EMR-documented COPD

d) **Exclusion Criteria**

- a. Cognitive disorder that in the judgment of the investigator impairs understanding of the study objectives or assessments (applicable for Option 1 only)
- b. Vulnerable populations, including prisoners and pregnant women

e) **Consent Process.** Patients admitted and who undergo cardiac catheterization for AMI will be identified via the EMR. If protocol Option 1 is being followed those with EMR-documented COPD will be approached for participation. They will be asked to provide written consent only after the objectives and risks of the study have been fully explained. Surrogate consent will not be permitted. The reasons for patients not being eligible for the study will be recorded. If protocol Option 2 is being followed a waiver of informed consent will be obtained from local IRBs for the initial EMR review and then telephone consent will be obtained after discharge. If Option 3 is being followed a waiver of consent will be obtained.

f) **Study Visit Schedule and Assessments**

- a. In-hospital visit and EMR review. All data elements will be obtained from the EMR except the self-reported COPD assessment which will be obtained during the hospitalization and after informed consent in protocol Option 1 and after discharge and phone consent in protocol option 2.
 - i. Demographics to include age, gender, race and ethnicity, height, weight
 - ii. Smoking status
 - iii. COPD assessment - year of diagnosis, home use of supplemental oxygen, self-reported history of spirometry being conducted, number of hospitalizations for COPD exacerbations in the year prior to admission, number of courses of antibiotics and/or steroids for COPD exacerbations in the year prior to admission. For protocol Option 1 this will be collected via self-report utilizing a questionnaire during the hospitalization. For protocol Option 2, this information will be obtained

after discharge and phone consent. For protocol Option 3 as much of this information as possible will be collected from review of the EMR.

- iv. Most recent forced expiratory volume (FEV1) and forced vital capacity (absolute and percent predicted) from EMR if documented in the 3 years prior to admission
- v. Comorbidity assessment to include cardiovascular disease and risk: history of hypertension, hyperlipidemia, coronary artery disease, prior MI, heart failure (ejection fraction prior to admission if available), percutaneous coronary intervention (PCI), coronary artery bypass grafting (CABG), peripheral vascular disease, stroke, diabetes mellitus, cirrhosis, asthma, obstructive sleep apnea, depression, anxiety, end-stage renal disease, cancer (type), organ transplantation (type)
- vi. Respiratory medication use on admission
- vii. Cardiovascular medication use on admission
- viii. Assessment of in hospital MI treatment: thrombolytics, PCI, CABG
- ix. Diagnosis of ST elevation MI (STEMI) or non-ST elevation MI (NSTEMI)
 - x. Initial post MI ejection fraction from inpatient echocardiogram
 - xi. Length of hospital stay
 - xii. Length of ICU stay
 - xiii. Need for intubation
 - xiv. Cardiogenic shock during hospital stay
 - xv. Discharge cardiovascular medications
 - xvi. Discharge disposition
- b. Phone calls (Option 1 only) and EMR review at 3 and 6 months
 - i. Vital status
 - ii. Date and cause of death if applicable
 - iii. Interval history of hospitalization and primary diagnosis (all events will be captured but hospitalizations for COPD exacerbations, recurrent MI, revascularization, or heart failure will be specifically queried)
 - iv. Interval history of treatment with steroids or antibiotics for exacerbations of COPD
 - v. Beta-blocker use and reason for discontinuation, if applicable Medical records will be collected for all admissions

g) Analytic and Statistical considerations.

- a. Analysis plan for Aim 1. The primary objectives of Aim 1 are to determine the number of admissions per year for AMI at our participating institutions and the prevalence of COPD in that population. These prevalence estimates will be calculated as a simple fraction. We will also compare the clinical characteristics of COPD patients discharged on a beta-blocker versus those not discharged on a beta-blocker using t-tests or chi-square tests (or Fisher's exact tests) as appropriate.
- b. Analysis plan for Aim 2. For the primary analysis we will compare the risk of death or all-cause hospitalization at 6 months for patients with AMI and COPD who were discharged alive on beta-blockers to that of patients not

discharged on beta-blockers. Secondary analyses will include comparisons of rates of hospitalization for COPD exacerbations, rates of hospitalization for recurrent MI or revascularization or heart failure, and rates of treatment with steroids and/or antibiotics for exacerbations. The primary analysis will be based on adjusted Kaplan–Meier survival curves that describe the probability remaining alive and out of hospital in those discharged versus not discharged on beta-blockers, while adjusting for the inverse probability of treatment weighting (IPTW) to reduce confounding. For all time-to-event analyses, the start time will be when the participant is discharged from the hospital.

Participants will be censored at 6 months post-discharge if no event occurred. The comparison of clinical characteristics between treatment groups conducted in aim 1 will be used to inform the calculation of the IPTW. We will use the adjusted log-rank test to compare the two curves. As secondary analyses, we will use both IPTW and adjusted Cox proportional-hazards models to assess the association between the beta-blocker prescription and death or re-hospitalization. Adjusted models will also include the covariates of race, sex, baseline age, smoking status, number of hospitalizations for COPD during the previous year, use of supplemental oxygen, presence of ejection fraction <40% at discharge. Assuming adequate frequencies between groups, we will stratify the models by beta-blocker use at the time of admission, presence of asthma, STEMI vs. NSTEMI, and site. Rates of exacerbation will be analyzed by IPTW negative binomial regression models and will be used to compare annualized rates of hospitalization.

- c. Sample size and power estimates. Prior data suggests that the prevalence of COPD in patients admitted with acute MI is between 13 and 25% depending on the population studied though these data have depended primarily on administrative coding (13, 16, 26-28). COPD is an independent risk factor for death following MI with estimates of in-hospital mortality of 12.5% versus 8.6% in those without COPD (28). Estimates for 1-year mortality for those with MI and COPD range from 14-25% versus 7-14% in those without COPD (29-33). Estimates of the benefit of beta-blockers in patients with COPD vary widely with studies demonstrating reductions in the risk of mortality between 9 and 50% (4, 13, 15, 16, 34). Data regarding the risk of re-hospitalization in COPD patients with MI and the association with beta-blocker use is scarce. However, the overall rate of readmission for recurrent MI, revascularization, heart failure, serious bleeding, as well as respiratory causes is 1.5-2 fold higher in those with COPD compared to those without the disease with a cumulative risk at 6 months between 25 and 45% (33, 35). Sample size calculations for the proposed study are therefore based on the following assumptions: The estimated sample size (number of patients with COPD and MI) assuming: Risk of death or re-hospitalization at 6 months in patients not prescribed beta blockers – between 32.5 to 37.5%; risk of death or re-hospitalization at 6 months in patients prescribed beta blockers – 25%; proportion of patients discharged on beta-blockers – between 45 and 85%; power of 80%; and type-I error of 5% is given in Table 1. With these assumptions our recruitment target is 500 patients with COPD and MI who

are discharged alive. Assuming in-hospital mortality of 12.5% (28) we plan to consent 571 patients to achieve this goal.

Table 1: Estimated sample size assuming power of 80%, $\alpha=0.05$, and risk of death or re-hospitalization at 6 months of 25% in group receiving beta blockers.

Risk in group not receiving beta blockers	Proportion of patients discharged on Beta-blockers										
	0.4	0.45	0.5	0.55	0.6	0.65	0.7	0.75	0.8	0.85	0.9
0.3	2528	2473	2471	2519	2622	2791	3053	3451	4083	5174	7401
0.325	1139	1119	1122	1148	1200	1283	1409	1600	1901	2420	3478
0.35	648	638	642	660	692	743	819	934	1115	1426	2058
0.375	418	413	417	430	453	488	540	618	741	951	1379

5. Data collection and handling. Data will be collected on study-specific case report forms (CRF) at each center and then data entered to the web-based system housed at the Data Coordinating Center (DCC) at the University of Minnesota.

- a. **Study Confidentiality and Privacy.** Study participants are identified by a unique number with a check digit for data integrity and an enrollment code consisting of the first letter of the participant's last name and the last two digits of their birth year. No PHI will be collected on study CRFs or transmitted to the DCC. Any identifying information that could be classified as PHI will be kept separate from the participant CRFs in a secure environment at the clinical center accessible only to study staff allowed access to PHI. Documents which contain PHI requested by the DCC will be properly de-identified prior to transmission so that no PHI can be obtained from the records.
- b. **Data Security.** The web-based data submission software is Oracle Application Server 11g Release 1. All data transmitted from the clinical sites to the DCC and from the DCC to the clinical sites is SSL encrypted. The cryptographic libraries used for SSL are designed to meet FIPS 140-2 Level 2 certification. The website is secured by individual usernames and strong passwords. Non-secure ports of all servers are located behind the DCC network firewall and accessible only under the following conditions: 1) a workstation physically present in the building and physically connected to the network 2) granted system access to the database server 3) a user name and strong password for that database server 4) a second username and strong password for database software 5) granted database access to data items. All non-essential ports of the database server and web servers are closed. Only one secure (HTTPS) port on the website server is open outside of the firewall; this port displays the login link to the secured website.

Clinical site staff may access individual data items for a given participant (only those in their own clinic) for review, but they are unable to download any participant data, aggregate it, cross reference an individual's data, or view participant data from another clinical site via the website.

All servers are physically located in a secured room which is accessible only by a key card; currently, only two system administrators, one financial administrator, and the Database Administrator have access to this room. In addition, the secured room is located in a secured suite which is also accessible only by key cards given to current University of Minnesota employees located in the suite. The building is locked and accessible only by University of Minnesota employees located in the building after business hours and on weekends.

The security administrator for Oracle RDBMS and Oracle Application Server is the Database Administrator. A network system administrator regularly monitors for occurrences of attempted access to the network by unauthorized users. Only the Database Administrator has access to sensitive software passwords. On-site backup of study data is performed nightly; off-site backups are taken twice weekly and stored at a secure University of Minnesota location, in a locked office in a secure suite. Additional redundancy is accomplished by storing duplicate database data files and control files on a separate server for disaster mitigation.

6. **Monitoring Plan:** Monitoring to ensure the study proceeds in compliance with the protocol is multifaceted including real time oversight by the local PIs and regular and real time monitoring of entered clinical data by staff at DCC as well as by an independent Observational Study Monitoring Board (OSMB). The OSMB will be made up of at least one cardiologist, one pulmonologist and a statistician and will meet every six months by teleconference. The responsibilities of the OSMB are to track performance of individual centers (including possible recommendations on actions to be taken regarding any center that performs unsatisfactorily); monitor overall recruitment, quality control, and data analysis; and oversee the overall scientific direction of the study. The DCC will prepare materials for the OSMB and will schedule meetings and prepare draft agendas. The DCC will also conduct monthly teleconferences throughout the study to review study enrolment and retention, procedures, adherence to protocol, and timeliness of data entry.

7. **Human subjects protection**

- a. Protection against risks. The procedures involved in this study are limited to data collection using questionnaires, review of EMR, and phone calls. Risks are limited to risks related to invasion of privacy and breach of confidentiality and are no greater than minimal. To protect against these risks, informed consent and will be obtained and filled out in private rooms and study visits will be conducted in private rooms (Option 1 only). All data will be stored on password-protected computers with access limited to authorized study personnel and adequate measures will be taken to maintain patient confidentiality at all times. All data collected from subjects will be labelled with a unique code that has no individually identifiable information. Patient information will be maintained as confidential to the extent permitted by law. The PI and other designated study staff (all who have been educated/trained on the protection of human subjects in research) will have access to identifiable private information of subjects, which may also be shared if requested with the UAB IRB, DOD, and others who are responsible for

ensuring compliance with laws and regulations related to research, including OHRP. All patient identifiers will be removed prior to any data analyses, or summary of data for publication in peer-reviewed journals.

- b. Potential benefits. There are no direct benefits to subjects who choose to participate in this observational study. Participants may have the satisfaction of participating in a research study that will potentially lead to improved treatment of COPD. The risks involved in the protocol are minimal, the potential benefits to our understanding of the overall risk-benefit of beta-blockers in COPD patients with acute MI are significant, and thus the overall risk-benefit favors the conduct of the study.
- c. Importance of knowledge gained. The results of proposed Aim 1 will provide data about the prevalence and clinical characteristics of COPD in the hospitalized population with MI in our network. The Aim will also provide an estimate of the number of annual admissions for patients with COPD and MI. Aim 2 will provide valuable information about the associations between beta-blocker use at discharge and the risk for all-cause mortality, recurrent ischemic events, and hospitalization for COPD exacerbation adjusting for baseline characteristics and COPD severity. Even though the parent BLOCK-COPD trial strongly indicated that patients with COPD and at risk for exacerbation should not be prescribed beta-blockers in the absence of an established indication for the drugs such as recent myocardial infarction or heart failure, questions remain about their use in the latter populations. The results of our proposed observational study would provide more robust and contemporary data regarding the overall risk-benefit of beta-blockers in COPD patients with acute MI and provide preliminary data about the feasibility of recruitment for a subsequent randomized trial.

References

1. Collaborators GBDCoD. Global, regional, and national age-sex-specific mortality for 282 causes of death in 195 countries and territories, 1980-2017: a systematic analysis for the Global Burden of Disease Study 2017. *Lancet*. 2018;392(10159):1736-88.
5. Westerik JA, Metting El, van Boven JF, Tiersma W, Kocks JW, Schermer TR. Associations between chronic comorbidity and exacerbation risk in primary care patients with COPD. *Respiratory research*. 2017;18(1):31.

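### Under Option 2, consent is taken by telephone after discharge but follow-up starts at discharge, so as written patients who die before the call drop out of the primary analysis (minor; small effect)

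*Combined protocol and SAP*

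**What the plan says.** All references are to the combined protocol and SAP.

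- **Consent as a criterion.** Section 4(c) lists as the first inclusion criterion "Willing and able to provide informed consent (applicable for Option 1 and 2 only".
- **Timing and waiver.** Section 4(e) says that at Option 2 sites a "waiver of informed consent will be obtained from local IRBs for the initial EMR review and then telephone consent will be obtained after discharge". No window is set for the call. The Option 3 waiver has no limit to the initial review: "If Option 3 is being followed a waiver of consent will be obtained".
- **Time zero.** Section 4(g)(b): "For all time-to-event analyses, the start time will be when the participant is discharged from the hospital". The primary endpoint is death or all-cause hospitalization by 6 months in patients discharged alive. Delayed entry is not mentioned, and there is no rule for patients who die or cannot be reached before consent.
- **Follow-up.** Section 4(a) gives Option 2 "post-discharge telephone consent and 2 follow up phone calls with EMR review at 3 and 6 months", while the heading of section 4(f)(b) limits the calls to Option 1. Specific Aim 2 says patients "will be followed, prospectively from the time of discharge using review of the electronic medical record".
- **Choice of option.** Section 4(a): "Option 1 or 2 is preferable if local guidance permits".

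**The concern.** The analysis population is everyone discharged alive, but an Option 2 patient joins it only by surviving to a call at an unspecified later date and agreeing. Someone who dies at home on day 5 belongs to the target population, has had a primary endpoint event, and cannot give consent. Those who do consent contribute time from discharge during which they could not have been observed to die. This is left truncation on one component of the primary endpoint.

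Readmissions before the call are not lost for patients who go on to consent, because their later EMR review can pick them up. The gap concerns patients who die, or cannot be reached, before consent.

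Nothing in the analysis plan repairs it. Inverse probability weighting on baseline covariates does not correct selection on survival after discharge. Stratification by site is conditional, is described for the models and not for the primary Kaplan-Meier curves, and cannot restore deaths that were never recorded. What is at stake is the absolute 6-month risk and, if early deaths differ by group in a particular way, the beta-blocker contrast.

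**Working it through.** **The plan's own figures.** Section 4(g)(c): 500/(1 - 0.125) = 571.4, matching the stated 571. Table 1 is reproduced by Schoenfeld's formula with HR = ln(1 - 0.25)/ln(1 - p0). At 35% vs 25% with 65% on beta-blockers, HR = 0.668; events = (1.960 + 0.842)²/(0.65 × 0.35 × 0.4037²) = 211.7; average risk = 0.65 × 0.25 + 0.35 × 0.35 = 0.285; N = 211.7/0.285 = 743, as tabulated. The 571 allows for in-hospital deaths after consent; nothing is allowed for Option 2 losses between discharge and consent.

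**Inputs.** From the plan: 6-month risks of 25% with beta-blockers and 35% without (within its 32.5-37.5%), N = 500, 1-year mortality 14-25%, in-hospital mortality 12.5%, mortality reduction 9-50%. Assumed, because the plan gives none of them: call at day 7 or day 28; constant hazard or a front-loaded Weibull hazard (shape 0.6); deaths 25% of first events; half the cohort in Option 2.

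**1. Proportional loss.** With H = -ln(1 - p) and f = (t/182)^shape, early event risk is e = 1 - exp(-H·f), early deaths d = 0.25e, and observed risk with Option 2 share s is (p - s·d)/(1 - s·d). The HR is the ratio of the H values.

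| Call, hazard | d, without vs with | Option 2 only (s = 1) | Half in Option 2 (s = 0.5) | HR |
|---|---|---|---|---|
| Day 7, constant | 0.41% vs 0.28% | 34.7% vs 24.8% | 34.9% vs 24.9% | 0.668 |
| Day 28, constant | 1.60% vs 1.08% | 33.9% vs 24.2% | 34.5% vs 24.6% | 0.668 |
| Day 28, shape 0.6 | 3.27% vs 2.23% | 32.8% vs 23.3% | 33.9% vs 24.2% | 0.667 |

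The risk falls by 0.2 to 2.2 points within Option 2 and by 0.1 to 1.1 points pooled. The risk difference goes from 10 points to between 9.9 and 9.5 within Option 2.

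**2. Early deaths tied to the plan's mortality range.** Take 3% early deaths without beta-blockers and s = 0.5.
- 50% reduction (1.5% with): 34.0% vs 24.4%, HR 0.674, log shift +0.009.
- 9% reduction (2.73% with): 34.0% vs 24.0%, HR 0.659, log shift -0.013.

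SE of the log HR = 1/sqrt(E·q(1 - q)), where q is the proportion on beta-blockers. At N = 500 and 1:1, E = 150 and SE = 0.163; at 85% on beta-blockers, E = 132.5 and SE = 0.243. The larger shift is 0.013/0.163 = 0.08 SE, or 0.05 SE at 85%. With every patient in Option 2 it is at most 0.17 SE.

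**3. Arbitrary imbalance, s = 0.5.** Early deaths of 3% without vs 1% with beta-blockers give HR 0.680 (shift 0.018, 0.11 SE). The reverse, 1% vs 3%, gives HR 0.640 (shift 0.042, 0.26 SE at 1:1; 0.54 SE if every patient were in Option 2).

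**4. How many deaths.** d = 1 - (1 - m)^((t/365)^shape) with m = 14-25% gives 0.3% (day 7, constant) to 6.0% (day 28, shape 0.6), or about 1 to 15 deaths among 250 Option 2 patients. If that mortality includes in-hospital deaths, m' = 1 - (1 - m)/0.875 = 1.7-14.3%, and the count is about 0 to 8.

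**The case against.** Four points can fairly be made against this.

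**The exclusion is inferred.** Section 4(f)(a) ties only the self-reported COPD assessment to telephone consent, section 4(f)(b) lists vital status under EMR review with no option limit, and Aim 2 speaks of EMR follow-up from discharge. A site could read these as allowing EMR outcomes for everyone. That stands as a reason for caution, but none of these passages says it covers unconsented Option 2 patients, and the consent criterion and the waiver wording point the other way. Similarly, "The reasons for patients not being eligible for the study will be recorded" is worded generally but sits in the Option 1 text, so whether it applies to Option 2 is unclear.

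**Every input that sets the size is assumed.** This stands. The plan does not say that any site uses Option 2; its preference for Options 1 and 2 over Option 3 means only that the share need not be small.

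**The comparison hardly moves.** This stands too, and keeps the point minor. The 0.26 SE figure needs three times as many early deaths in the group with the lower 6-month risk, an assumption with no source in the plan.

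**Simply retaining unreached patients creates a new problem.** Section 4(g)(b) adjusts for prior-year COPD hospitalizations and supplemental oxygen. Under section 4(f)(a) these are self-reported after consent in Option 2. EMR values for those who died early and self-report for the rest would make covariate source depend on outcome. This stands and shapes the fix.

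A reader might also infer immortal-time bias in favour of beta-blockers. The documents do not support that: exposure is fixed at discharge in both groups, both face the same consent gap, and the direction of any effect on the hazard ratio is not determined.

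**Conclusion.** The point holds as a minor one. Following sections 4(c), 4(e) and 4(g)(b) as written leaves Option 2 deaths before the call out of the analysis and biases the Option 2 Kaplan-Meier risk downward, by about 0.2 to 2.2 points within Option 2 and 0.1 to 1.1 points with half the cohort there. These figures rest on the assumed call day, hazard shape, death fraction and Option 2 share; with no Option 2 patients the effect is nil. Option 3, and in-hospital consent under Option 1, do not have this gap.

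It would be tempting to conclude that the beta-blocker comparison is materially compromised. The plan's figures do not show that: the hazard ratio stays at 0.667-0.668 under proportional loss, and within the plan's 9-50% mortality range the shift is at most about 0.08 SE with half in Option 2. The calculations cover deaths only; the effect of losing patients who are alive but not reached is not quantified. The point is still worth raising because outcomes outside the waiver may not be recoverable later.

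**What to change.** 1. In the Option 2 waiver request to local IRBs, ask also for EMR vital status and hospitalizations from discharge.
2. State in section 4(g)(b) that all eligible Option 2 patients discharged alive are in the primary analysis, and set a window for the call.
3. State a rule for patients who are reached and refuse. Dropping them while keeping every early death raises risk slightly: with 20% refusal within Option 2, (d + 0.8(p - d))/(d + 0.8(1 - d)) gives 35.1% vs 25.1% (day 7, constant hazard) to 35.5% vs 25.4% (day 28, shape 0.6), HR 0.668.
4. Take the COPD-history covariates used in the weights and models (prior-year COPD hospitalizations, supplemental oxygen) from the EMR for all Option 2 patients, reached or not, and keep self-report as supplementary.
5. Reconcile sections 4(a) and 4(f)(b) on whether Option 2 has follow-up calls.

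If the wider waiver is refused: record deaths and non-contacts before consent by discharge beta-blocker status where permitted, present results by enrollment option, and add delayed entry at consent as a sensitivity analysis only. As a primary analysis, delayed entry would discard e/p of Option 2 first events, about 4-5% (day 7, constant hazard) to 36-37% (day 28, shape 0.6), and would rely on Option 1 and 3 patients to represent the early period.

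The cost is an added request at each Option 2 site's IRB, somewhat poorer COPD-history data from the EMR, and slightly more analysis.
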